8.2.2 Secondary analysis

- a) For the secondary end point of recurrence rate defined by 10-week biopsy, the Chi-squares test is used to test the rate difference between the two arms, and a logistic regression is needed to further adjust potential covariates, e.g. total BCG therapy dose.
- b) For the secondary end point of the total dose of intravesical therapy administered over 6 weeks, we consider the two-sample t test and/or sum rank test to test the difference between two arms. If genistein supplement works by reducing symptoms and maintaining the therapy dose, we expect to see a higher total therapy dose in its arm than in the placebo arm.
- c) We will also explore the change of IPSS score over time by the GEE model in which the repeated measurements of IPSS score are treated as outcome. Treatment, time, interaction between treatment and time, and intravesical therapy dose enter the model as predictors and time-dependent covariate.

9. Adverse Event Reporting:

According to 21 CFR 312.32, *Adverse event* means any untoward medical occurrence associated with the use of a drug in humans, whether or not considered drug related. A *Serious adverse event* or *serious suspected adverse reaction* is an adverse event or suspected adverse reaction is considered "serious" if, in the view of either the

investigator or sponsor, it results in any of the following outcomes: Death, a life-threatening adverse event, inpatient hospitalization or prolongation of existing hospitalization, a persistent or significant incapacity or substantial disruption of the ability to conduct normal life functions, or a congenital anomaly/birth defect. Important medical events that may not result in death, be life-threatening, or require hospitalization may be considered serious when, based upon appropriate medical judgment, they may jeopardize the patient or subject and may require medical or surgical intervention to prevent one of the outcomes listed in this definition. Examples of such medical events include allergic bronchospasm requiring intensive treatment in an emergency room or at home, blood dyscrasias or convulsions that do not result in inpatient hospitalization, or the development of drug dependency or drug abuse.

Adverse events will be recorded at each study visit via direct patient communication as well as through patient questionnaires. The severity of the AEs will be graded according to NCI CTCAE Version 4.0. Subjects with toxicities of Grade 3 or higher will be immediately discontinued from the study pill for the remainder of treatment. Any BCG intravesical therapy modifications will be done according to doctor analysis with an effort on alleviating toxicities as needed. In order to be evaluable, patients will need to receive at least three BCG instillations. If BCG treatment is interrupted or discontinued, only IPSS scores will be obtained via phone call. If a SAE occurs, we will promptly report it to our IRB upon discovery and follow the subject until the SAE is resolved. Adverse events will be reported to the IRB according to their requirements.

IND safety reports will be sent to the FDA in accordance with 312.32 the FDA's *Guidance for Industry and Investigators: Safety Reporting Requirements for INDs and BA/BE studies*. IND safety reports will document any aggregate adverse events, adverse reactions suspected adverse reactions, or serious adverse events. If the event is considered to be unexpected fatal or life-threatening, the IND safety report will be sent as soon as possible and within 7 business days of the investigator being notified. If necessary, the investigator will report any serious or life-threatening event initially by facsimile or telephone prior to formal submission. IND safety reports will also be submitted to the FDA if any related safety information is released from other sources. Any nonserious adverse events will be reported to the FDA in aggregate on an annual basis.

10. Data and Safety Monitoring Plan (DSMP):

Once the study has reached 50% accrual, investigators will plan to initially evaluate the results. A group of physicians from the Winship Cancer Institute at Emory University will review the data and questionnaires to see how patients are reacting to the genistein supplement arm or whether there are drug compliance issues, such as failure to take the pills per protocol. If the genistein supplement arm has statistically significant toxicities reported or greater degree of bladder cancer biopsies then we will immediately

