BCG intravesical therapy is a form of immunotherapy commonly used to prevent the recurrence of noninvasive bladder cancer, which occurs in approximately 50-80% of bladder cancer patients within 5 years. 10-20% of all superficial bladder cancer patients will progress beyond superficial recurrence within 5 years. Smoking, poor diets, and large body weights are all potential risk factors for recurrence, but there is also a high propensity for bladder cancer recurrence in general due to its aggressive nature. As treatment, BCG intravesical therapy is instilled in the bladder using a urinary catheter. The intravesical therapy remains in the bladder for about two hours until the patient urinates. The treatment is usually once a week for six weeks and then repeated every 3-6 months for two years. However, intravesical therapy typically causes urinary tract symptoms, such as pain, frequency, burning, inflammation, and bleeding in patients. Symptoms may occur after the very first treatment or become worse over time as therapy continues. As a result, the dose of therapy is often reduced so that symptoms can be treated symptomatically with antibiotics or pain medication. Dose reduction is generally done in 50% increments, and the decision to reduce the treatment dosage is often subjective based on each patient's perception of symptoms.

The isoflavone genistein (4,7,4'-trihydroxyisoflavone) is a phytoestrogen found in high levels in soy products and can be taken as a nutritional supplement for its antioxidant benefits and its estrogenic properties. The genistein supplement is sold over the counter and has less soy isoflavone than commonly found in many healthy diets. For comparison, an 8 ounce glass of soy milk has 15 mg of genistein. Studies have used up to 300 mg of genistein supplement daily, and it has been shown as safe, well accepted, and well tolerated with no known significant toxicities.

Recent epidemiologic reports show that some Asian countries with high soy consumption have a smaller incidence of prostate carcinoma and studies suggest it might be due to the anticancer effects of soy. A study of 41 subjects in 2003 showed that there was a significant slow in the rate of PSA rise in prostate cancer patients after taking 100 mg of genistein supplement daily for 6 monthsⁱ A recent study of 52 subjects in 2010 showed that the short-

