4.2 Secondary objective

- a) A secondary study endpoint will be the presence of cancer and the rate of recurrence as determined by the 10-week biopsy or subsequent standard follow-up visits.
- b) A second secondary study endpoint will be the total dose of intravesical therapy administered over the 6 weeks of treatment. If subjects develop fewer urinary tract symptoms as a result of the genistein supplement, then hypothetically, intravesical therapy dosing would not have to be reduced as much. This will be measured by looking at the level of dose reduction for each treatment week and comparing it across the two arms.

5. Study Design and Methods:

At the pre-operative office visit before intravesical therapy, eligible patients will be screened and enrolled into the study by going through the consent process and signing the consent and HIPAA forms. Each patient will need to report all other medications so that the study team can assess whether certain medications might affect trial outcome.

Patients will be randomized into Arm 1 (placebo) or Arm 2 (genistein supplement) at a ratio of 1:1 stratified by one dichotomized prognostic factor, age. The dichotomization will take place based on whether they are age 60 and above or whether they are age 59 and below. This will allow for similar age groups to be placed in each arm, so that the degree of urinary symptoms while receiving treatment is not skewed depending on the patient's age.

Patients are treated with intravesical therapy once a week for 6 weeks and then return to the office approximately four weeks later for a post-operative visit and biopsy, as is standard care. Study subjects will take their genistein or placebo tablets for a total of 10 weeks, which includes the length of their treatment, as well as the 4 weeks before the post-op visit. Each patient will fill out an International Prostate Symptom Score (IPSS) questionnaire at their baseline office visit when consented. Patients will fill out an IPSS questionnaire at each subsequent intravesical therapy session and their final one-month follow-up appointment (at 10 weeks) either in person or via phone call with a study team member. The IPSS questionnaire will gauge their urinary symptoms throughout their therapy and provide measurable symptom scores for the two arms. The biopsy at 10 weeks, as well as standard 3 months follow-up appointments, is standard care for superficial bladder patients and will help determine cancer rate of recurrence.

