	Baseline	BCG Week 1-6 ^b	10 Week ^c
Placebo Arm	
 • Screening (Physical Exam,^a Vitals,^a complete blood count and serum chemistry analyses, ^a Urine Dipstick, IPSS Questionnaire) • Enrollment • Randomization 	
 • Urine Dipstick, Interval History, Vitals, IPSS Questionnaire* • BCG Intravesical Therapy • 6 weeks of placebo (30 mg, PO TID) • Continue taking placebo for remaining 4 weeks before biopsy 	
 • Bladder Cystoscopy (Biopsy recommended, but not mandatory) • Urinary cytology (if indicated) • Interval History • IPSS Questionnaire* • Physical Exam • Vital signs • Complete blood count and serum chemistry panel is recommended, but not mandatory
Genistein Supplement Arm	
 • Screening (Physical Exam, ^a Vitals,^a complete blood count and serum chemistry analyses, ^a Urine Dipstick, IPSS Questionnaire) , • Enrollment, • Randomization 	
 • Urine Dipstick, Interval History, Vitals, IPSS Questionnaire*, • BCG Intravesical Therapy • 6 weeks of genistein Supplement (30 mg, PO TID) • Continue taking genistein Supplement for remaining 4 weeks before biopsy 	
 • Bladder Biopsy (pathology) • Urinary cytology • Interval History • IPSS Questionnaire* • Physical Exam • Vital signs • Complete blood count and serum chemistry panel is recommended, but not mandatory

^a Within 2 months before the first dose of study treatment.

^b A range of 7 days before or after the scheduled visit is allowed or per standard of care. If BCG treatment is interrupted or discontinued Urine Dipstick, Interval History, and Vitals may not be collected per standard of care.

^c A range of 2-3 weeks before or after the 10 week is allowed or per standard of care.

*IPSS Questionnaire may be collected via phone call.

6. Participant Selection:

44 patients will be enrolled in the trial, with 22 subjects on each arm. Potential subjects will be superficial bladder cancer patients in the Department of Urology who are scheduled for their standard-of-care BCG intravesical therapy.

Inclusion Criteria:

1. Male or female gender
2. 18 years or older
3. Diagnosis of superficial bladder cancer
4. Scheduled for induction BCG intravesical therapy
5. Willing and able to give blood sample
6. Willing and able to fill out a pill diary to ensure compliance
7. Willing and able to sign informed consent

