8.1 Power analysis

We hypothesize that, at 6 weeks, the symptom score will increase by 6 (SD = 3.5) relative to the baseline in the placebo arm, while it will only increase by 3 (SD = 3.5) in the synthetic genistein supplement arm. A sample size of 20 patients in each arm can reach 83% power to detect the hypothesized difference at the significance level of 0.05 by one-sided Mann-Whitney test.

In an effort to reach a sample size of 20 patients on each arm, we also hypothesize that there will be a 10% drop-out or non-compliance rate. We will accrue 44 patients, 22 subjects on each arm, for this study with the expectation that 10% will drop out. With a 10% drop out rate included, this would result in a total of 40 compliant patients.

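### The 10-week recurrence analysis plans no confidence interval and no method for sparse events, and its only named covariate is measured after randomisation

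*Combined protocol and SAP*

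**What the plan says.** Section 8.2.2(a) fixes the timing of the endpoint: "For the secondary end point of recurrence rate defined by 10-week biopsy". It then states that "the Chi-squares test is used to test the rate difference between the two arms", and that "a logistic regression is needed to further adjust potential covariates, e.g. total BCG therapy dose". It does not name an estimation method, limit the number of covariates, plan an interval for the difference, or say what happens if an arm has no events. Section 8.2.1, by contrast, plans a 95% confidence interval for the primary IPSS change.

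Section 4.2(a) describes the endpoint more widely, as "the presence of cancer and the rate of recurrence as determined by the 10-week biopsy or subsequent standard follow-up visits". The only recurrence figure in the documents is in the Introduction and Background (section 2), where recurrence is something "which occurs in approximately 50-80% of bladder cancer patients within 5 years". No 10-week rate or event count is given. Section 8.1 plans for 20 analysed patients per arm.

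**The concern.** Ordinary logistic regression is fitted by maximum likelihood unless something else is specified. When one arm has no events, the log odds ratio for treatment has no finite maximum-likelihood estimate: the odds ratio goes to zero or infinity, or is undefined if neither arm has an event. Wald tests and intervals then mean nothing. A 40-patient trial with a 10-week binary endpoint is exposed to this, and the plan has no fallback. The chi-square test can still be computed in most such cases, but it gives a p-value with no estimate of size or precision.

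The named covariate raises a separate problem. Total BCG dose accrues after randomisation. Section 8.2.2(b) says that, if genistein works by easing symptoms, dose should be higher in its arm. A model that holds dose fixed may therefore remove part of the treatment effect it is meant to estimate.

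Improved efficacy is in the trial's title and hypothesis, so readers will look to this result even though it is secondary.

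**Working it through.** **The plan's own figure.** Section 8.1 says "A sample size of 20 patients in each arm can reach 83% power to detect the hypothesized difference", for the IPSS change. With a difference of 3, SD 3.5, one-sided 0.05, and 20 × 3/π = 19.1 effective patients per arm for Mann-Whitney efficiency, the noncentral t gives 83.0%. A direct simulation gives 81.8%. The figure reproduces, but it concerns the primary endpoint. Recurrence has no stated power.

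**Events at 10 weeks.** Inputs: five-year recurrence r of 50% and 80% (section 2) and 40 analysed patients (section 8.1). Assumption: constant hazard. The 10-week rate is 1 − (1 − r)^(10/260.9).
- r = 0.5: 2.6%, so 40 × 0.0262 = 1.05 events.
- r = 0.8: 6.0%, so 40 × 0.0598 = 2.4 events.

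Expected events per arm are then about 0.5 to 1.2, too few for the usual chi-square approximation to be trusted. The 10% to 30% rates below are assumptions, added because events may come early.

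**Chance that at least one arm has no event.** With a = (1 − p₁)^20 and b = (1 − p₂)^20, the probability is a + b − ab. The last column is the binomial probability of at least 4 events among 20 placebo patients.

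| Assumed 10-week rate | Expected events in 40, equal arms | An arm with no event, equal arms | Same, genistein rate halved | At least 4 of 20 on placebo |
|---|---|---|---|---|
| 2.6% | 1.05 | 83% | – | – |
| 6.0% | 2.4 | 50% | 68% | 3% |
| 10% | 4 | 23% | 44% | 13% |
| 15% | 6 | 8% | 24% | 35% |
| 20% | 8 | 2% | 13% | 59% |
| 30% | 12 | 0.2% | 4% | – |

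Example at 10%: 0.9^20 = 0.1216, and 2 × 0.1216 − 0.1216² = 0.228. With the genistein rate halved to 5%: 0.1216 + 0.3585 − 0.0436 = 0.436. At the two document-based rates, 35% and 8% of trials would have no event in either arm.

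**Adding dose to the model.** I simulated logistic fits on arm plus total dose, 800 runs per setting with equal arms. I assumed that each of the six instillations has a 30% chance of being halved, unrelated to outcome. There was no finite estimate in about 84%, 49%, 24% and 2.5% of runs at rates of 2.6%, 6%, 10% and 20%. This is close to the empty-arm probabilities.

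**Precision when the estimate is finite.** The median ratio of upper to lower 95% limit for the treatment odds ratio was about 27 at a 20% rate and 17 at 30%. A 27-fold ratio around an estimate of 0.5 runs from 0.5/√27 = 0.10 to 0.5 × √27 = 2.6.

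**Chi-square threshold.** Pearson, uncorrected, 20 per arm:
- 3 v 0: 40 × (3 × 20)² / (3 × 37 × 20 × 20) = 3.24, p = 0.072.
- 4 v 0: 40 × (4 × 20)² / (4 × 36 × 20 × 20) = 4.44, p = 0.035.

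With no genistein events, at least 4 placebo events are needed for two-sided p < 0.05.

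**Denominator.** The schedule in section 5 lists, for the placebo arm, "Bladder Cystoscopy (Biopsy recommended, but not mandatory", so the number with a biopsy result may fall below 20.

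**The case against.** The strongest reply is that the event rate is unknown. The documents give no 10-week rate, and the constant hazard is the reviewer's assumption. Section 4.2(a) counts presence of cancer as well as recurrence, and Tis patients are enrolled, so residual disease at biopsy may count and events could be far more frequent. At 20% or more in both arms an empty arm is rare. Section 4.2(a) also admits later visits; under the same constant hazard these would give about 5 to 11 events by one year and 10 to 19 by two. This stands as a limit on the size of the problem. It does not supply a fallback, and 8.2.2(a) still fixes the analysis at 10 weeks.

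Three stronger readings are tempting and are not supported:
- A reader might infer that the protocol's own rates imply a handful of events. They do so only if recurrence accrues evenly, which the documents do not say.
- A reader might infer that the efficacy result rests on the logistic model, or that its estimate fails in more than half of trials even at a 10% rate. Chi-square is the stated test and the regression is a further adjustment. Maximum likelihood is the default reading, not the plan's wording. Failure rates of about 53%, 33% and 23% at 10%, 15% and 20% need an added age term, which 8.2.2(a) does not name, and an assumed 80/20 age split. The excess comes mainly from the age coefficient diverging, and the treatment estimate can stay finite.
- A reader might infer that the p-value can never favour genistein. That holds only with fewer than 4 placebo events. If genistein prevented every recurrence, the chance of 4 or more on placebo would be 35% at a 15% rate and 59% at 20%.

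It is also fair to say that this is a secondary endpoint without a power claim in a 44-patient phase II trial.

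**Conclusion.** The point holds as a gap in the plan for a secondary endpoint. Section 8.2.2(a) has no interval, no sparse-data method, an open covariate list, and one named covariate that treatment is expected to change. How often the treatment odds ratio would lack a finite estimate depends on an unstated rate. It is about 50-83% if the five-year rates accrue evenly, and about 23%, 8% and 2% at assumed common rates of 10%, 15% and 20%. If genistein halves those three rates it rises to 44%, 24% and 13%, so the analysis is more fragile when the hypothesis is true. Poor precision does not depend on the low-rate assumption, since it persists at 20-30%. The objection to adjusting for dose does not depend on the event rate at all. All figures assume 20 analysed patients per arm. The primary IPSS analysis is unaffected.

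**What to change.** In 8.2.2(a):
- Make the main result the risk difference between arms with a Miettinen-Nurminen 95% confidence interval, which can be calculated when an arm has no events. Report the chi-square p-value beside it.
- Fit the adjusted model by Firth penalised likelihood with profile-likelihood intervals, limited to treatment plus one baseline covariate: the age stratum (60 and above v under 60) already used for randomisation.
- Keep any model that includes total BCG dose as exploratory, and say that dose is measured after randomisation and may carry part of the treatment effect.
- State that a non-significant result does not show equal recurrence.

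The cost is SAP wording and standard software options; sample size, visits and the primary analysis do not change. Firth estimates shrink slightly toward no effect. No method recovers information from one or two events: the change ensures that the trial reports an interpretable estimate with honest uncertainty, and it does not add power.

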Title: PHASE II RANDOMIZED PLACEBO-CONTROLLED CLINICAL TRIAL OF GENISTEIN IN REDUCING THE TOXICITY AND IMPROVING THE EFFICACY OF INTRAVESICAL THERAPY

Study Principal Investigator: [name] MD

Study Sponsor: [name]

Study Co-Principal Investigator: [name] PhD

Study Supporter: DSM Nutritional Products

Version Date: 16 Jul 2019

Schema:

E n r o ll m e n t	44 TaT1 Tis superficial bladder cancer patients scheduled to receive BCG intravesical therapy will be consented Estimated Timeline: until 44 subjects are enrolled (approximately 2 years)	R a n d o m iz a ti o n	Arm 1: BCG intravesical therapy with placebo pills for 10 weeks (22 subjects) Arm 2: BCG intravesical therapy with 30 mg genistein supplement PO TID for 10 weeks (22 subjects)	F o ll o w - u p	Arm 1: Followed-up according to standard after-treatment care: one-month post-treatment appointment and subsequent doctor visits. Arm 2: Followed-up according to standard after-treatment care: one-month post-treatment appointment and subsequent doctor visits.
--	---	---	--	---------------------------------------	--

Patients will take either 30 mg tablets of placebo or genistein supplement PO TID, for 6 weeks during BCG intravesical therapy and will continue for 4 weeks following therapy.

1. Abstract:

Patients who are treated with BCG intravesical therapy for TaT1 Tis superficial bladder cancer often develop adverse effects (urinary tract symptoms) which limit the dose (and therefore the efficacy) of therapy and result in poor quality of life. Genistein is a nutritional supplement with anti-inflammatory properties which might help alleviate adverse effects of intravesical therapy that are due to inflammation. Additionally, genistein also has anti-tumor and immunopotentiating properties and has been shown to have no known side effects. Our hypothesis is that genistein given together with BCG intravesical therapy will reduce its adverse effects and improve the efficacy of therapy. Patients (N=44) scheduled for intravesical therapy will be randomly assigned to take 30 mg tablets of genistein supplement (N=22) or placebo (N=22) PO TID during therapy and one month post therapy.

2. Introduction and Background:

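### The recurrence logistic model and the IPSS GEE adjust for BCG dose, a post-randomisation endpoint, so their genistein coefficients do not estimate the randomised effect

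*Combined protocol and SAP*

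**What the plan says.** Section 4.2(b) makes BCG dose an outcome: "A second secondary study endpoint will be the total dose of intravesical therapy administered over the 6 weeks of treatment". It reasons that with fewer urinary symptoms, "then hypothetically, intravesical therapy dosing would not have to be reduced as much". Section 8.2.2(b) gives the expected direction: "If genistein supplement works by reducing symptoms and maintaining the therapy dose, we expect to see a higher total therapy dose in its arm".

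The protocol also describes the chain on either side of dose. The Abstract speaks of "adverse effects (urinary tract symptoms) which limit the dose (and therefore the efficacy) of therapy". The Introduction says of the urinary symptoms: "As a result, the dose of therapy is often reduced so that symptoms can be treated symptomatically". Section 9 leaves BCG modifications to the physician, with the aim of easing toxicity.

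Two models in section 8.2.2 then adjust for dose:

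- In (a), after a chi-square test of recurrence, "a logistic regression is needed to further adjust potential covariates, e.g. total BCG therapy dose". No other covariate is named.
- In (c), for the GEE on repeated IPSS scores: "Treatment, time, interaction between treatment and time, and intravesical therapy dose enter the model as predictors and time-dependent covariate". This is the only longitudinal IPSS model planned.

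The plan contains no GEE without dose. It does not describe either model as a mediation or direct-effect analysis, and it does not say how the arm coefficient is to be read. For the GEE it gives neither the working correlation nor which visit's dose is entered.

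**The concern.** Randomisation makes the arms comparable at baseline. Conditioning on something that treatment changes afterwards gives up that comparability and changes the question.

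For recurrence, dose is a mediator on the protocol's own account: genistein eases symptoms, dose is maintained, efficacy improves. Holding dose fixed leaves that route out of the arm coefficient.

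For IPSS the position is worse. Dose is cut in response to earlier scores and influences later ones, so it is partly a consequence of the outcome being modelled. The arm and arm-by-time coefficients can then be wrong in either direction.

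What is at stake is interpretation. A dose-adjusted odds ratio near 1 could be taken as evidence against genistein when the model has only subtracted the proposed mechanism. The only analysis of IPSS over time could understate or overstate the effect.

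**Working it through.** **1. The plan's own figure, used for scaling.** Section 8.1 assumes IPSS rises of 6 and 3 (SD 3.5), 20 per arm, one-sided 0.05, Mann-Whitney test, 83% power. With effective n' = 20 × 3/π = 19.1, power = Φ(3/(3.5√(2/19.1)) − 1.645) = Φ(2.649 − 1.645) = 84.2%. The noncentral t gives 83.0% and direct simulation 82.3%. The 83% is reproduced, and dose plays no part in it.

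**2. Recurrence, exact calculation.** The documents give no rates, so all inputs are assumed: 20% recurrence at full dose; dose reduced in 30 vs 15%, 50 vs 20% or 60 vs 20% of placebo vs genistein patients; odds ratio 2 to 4 for reduced against full dose.

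For an arm with a share r reduced, p = (1 − r)·p_full + r·p_reduced. Take 50 vs 20% and a dose odds ratio of 3, with no direct effect of genistein:

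- Full-dose odds are 0.25, so reduced-dose odds are 0.75 and p_reduced = 0.4286.
- Placebo: 0.5 × 0.20 + 0.5 × 0.4286 = 0.3143.
- Genistein: 0.8 × 0.20 + 0.2 × 0.4286 = 0.2457.
- Unadjusted odds ratio: (0.2457/0.7543)/(0.3143/0.6857) = 0.71, log −0.34.
- Within each dose level the arms have equal risk, so the adjusted odds ratio is 1.00 and 100% of the effect is removed.

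Now add a direct log odds ratio of −0.5. The genistein odds are multiplied by 0.6065, giving risks of 0.1317 and 0.3127 and an overall 0.8 × 0.1317 + 0.2 × 0.3127 = 0.1679. The unadjusted log odds ratio is −0.82 and the adjusted one −0.50, so 1 − 0.50/0.82 = 39% is removed.

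| Direct log OR | Share of arm log OR removed, over the grid |
|---|---|
| 0 | 100% |
| −0.25 | 31–68% |
| −0.5 | 18–51% |
| Any, if dose does not affect recurrence | 0% |

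A second set-up used continuous total dose (mean gain 0.45 to 1.14 full-dose equivalents) and an effect wholly through dose. Odds ratios of 0.87 to 0.33 without dose became 0.99 to 1.00 with it.

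Precision is poor in either analysis. At 20 per arm the standard error of 0.3143 − 0.2457 = 0.0686 is 0.1416, so z = 0.484 and two-sided power is about Φ(0.484 − 1.96) = 7%.

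**3. IPSS GEE, simulation.** The scale follows section 8.1 (rise 6.1 vs 3.1, SD 3.5 and 3.2). Assumed: symptoms accumulate with cumulative dose, and dose is halved (minimum 25%) when IPSS has risen by more than 7. There were 20,000 patients per scenario and time was categorical. The target is the arm difference in change from week 1 to week 6; its true value, and the fit without dose, is −3.06.

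| Dose entered | Independence | Exchangeable | AR-1 |
|---|---|---|---|
| Same visit | −2.08 (32% smaller) | −1.56 (49% smaller) | −1.19 (61% smaller) |
| Previous visit | −3.01 (2% smaller) | −3.15 (3% larger) | −4.01 (31% larger) |

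Over triggers of 5, 6 and 7 points the range was 58% smaller to 7% larger under independence or exchangeable correlation, and 76% smaller to 46% larger with AR-1 included.

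At 20 per arm (1,500 trials, trigger 6), one-sided 0.05 power was 91% without dose. It was 65% or 52% with same-visit dose, and 84% or 90% with previous-visit dose (independence or exchangeable). The Mann-Whitney test, which ignores dose, had 89%.

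**4. A milder mechanism.** Here dose cuts were probabilistic and driven by the previous week's score, with independence working correlation. The dose-adjusted week-6 contrast was −2.79 against a true −2.41, and in another case −2.86 against −3.00. In the first case the fit without dose gave −2.55, so 0.14 of the 0.38 gap comes from fitting time as linear and 0.24 from adding dose. When dose did not depend on symptoms, the adjusted and true values agreed at −3.00.

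**5. Null check.** With no genistein effect, all GEE estimates in the step 3 set-up lay within 0.07 of zero. The problem is distortion of a real effect, not a false positive.

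**The case against.** The strongest reply is that nothing confirmatory is touched. The primary Mann-Whitney test and the chi-square test use no dose, and the primary analysis already gives the week-6 contrast unadjusted. The GEE is called exploratory, and dose enters the logistic model only as an example. The Abstract also claims that "genistein also has anti-tumor and immunopotentiating properties", so asking whether genistein acts beyond maintained dose is legitimate. All of this stands, and it limits the severity.

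The size is also open to challenge. The large GEE distortions need same-visit dose and a fixed IPSS cut-off, whereas the Introduction describes dose reduction as often subjective. With decision noise of SD 3.5 points added in a similar model, same-visit attenuation was 11% (independence) or 21% (exchangeable); with SD 7 it was about 0% or 7%. Previous-visit dose moved the contrast by 5% or less there. Noise also makes cuts more frequent and narrows the arm difference in dose, so this shows the bias shrinking, not that it is absent. For recurrence, the 0.34 shift in log odds ratio is about half its standard error of 0.71 at 20 per arm.

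What does not stand is that the plan already covers the point. Calling a model exploratory does not say what its arm coefficient estimates. A direct-effect question is a different one and needs mediation assumptions that the plan never states.

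**Conclusion.** The concern holds, as a change that should be made but does not threaten the primary result. The principle is certain: the dose-adjusted coefficients answer a different question from the randomised comparison.

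The size rests on assumptions. For recurrence, adjustment removes all of the arm effect if genistein works only through dose, part of it (18–68% in the grid) if it also acts directly, and nothing material if dose does not affect recurrence. For the GEE, neither direction nor size can be fixed from the plan. They depend on the working correlation, the dose visit and how dose decisions are made, and results ranged from negligible to more than half of the effect. The distortion requires genistein to change BCG dose, which is the trial's own hypothesis, so it is expected when the treatment works as proposed. Neither recurrence analysis is likely to be decisive at this sample size.

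**What to change.** - **8.2.2(a):** keep the chi-square test. Adjust the logistic model only for pre-randomisation covariates, such as the age stratum.
- **8.2.2(c):** estimate the treatment effect from a GEE with arm, time and arm-by-time, plus pre-randomisation covariates if wanted, without BCG dose. State the working correlation.
- **8.2.2(b):** report BCG dose as an outcome in its own right, as already planned.
- **If dose-adjusted fits are kept:** label them supportive, state which visit's dose is used, and say that they do not estimate the effect of genistein as randomised.

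The cost is analysis wording: one covariate removed from two models, or a dose-free fit and a label added. No new data, patients or staff are needed.
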